9.2.2 Physical Examination

A physical examination will be performed by the investigator as per the Study Flow Chart (Appendix 1) at every visit in accordance with local practices. This examination will be symptom-directed, i.e., a standard panel of body systems will not be assessed unless indicated by patient. For example should the patient report to the investigator the presence of ‘rash’ then

the skin would be evaluated. It is not required that additional body systems are assessed unless clinically warranted. Any clinically significant abnormal results should be recorded in the CRF. Changes in findings of the physical examination compared with the baseline examination should be recorded as an AE.

9.2.3 Vital Signs

Vital signs measurements will be performed as per the Study Flow Chart (Appendix 1) at every visit. Measurements to be taken include:

- Blood pressure: will be performed as supine (after at least 5 minutes of rest) systolic and diastolic blood pressure (in mmHg)
- Heart rate: taken at rest (in bpm)
- Temperature: will be taken as per clinic practice. Temperature and route will be recorded in the CRF.

Vital signs measurements will be performed before any blood samples are taken. All new findings or changes to previous findings considered clinically significant will be recorded in the CRF as an AE if the finding is made after the patient has signed the ICF.

9.2.4 Clinical Laboratory Safety Tests: Haematology, Serum Biochemistry, and Urinalysis

Blood and urine samples will be taken as per the Study Flow Chart (Appendix 1) for routine haematology, serum biochemistry and urinalysis tests. All samples will be analysed in the central laboratory.

Table 2: Clinical Laboratory Safety Tests

Haematology:	Full blood count to include red cell count, haemoglobin, haematocrit, white cell count, differential white cell count, platelet count and.
Serum biochemistry:	Urea (blood urea nitrogen; BUN), creatinine, uric acid, total bilirubin, potassium, , alkaline phosphatase (ALP), aspartate aminotransferase (AST), alanine aminotransferase (ALT), lactate dehydrogenase (LDH), creatine phosphokinase (CPK), albumin, total protein, cholesterol, triglycerides, glucose.
Urinalysis:	pH, protein, glucose, blood.

If required a Follicle-Stimulating Hormone (FSH) test to confirm non-child bearing potential will be carried out at screening only.

Details of the volume of blood or urine to be taken, sample preparation and handling are contained in a separate Laboratory Procedures Manual. Laboratory results will be reviewed for clinically significant values by each investigator following sample analysis and verification. The report must be signed and dated by the investigator before insertion in the CRF.

Additional blood may be required for repeats of safety laboratory test.

9.2.5 Pregnancy Test

For female patients of childbearing potential, a pregnancy test will be carried out at screening and Week 8 /Visit 6/ET visit, as per the Study Flow Chart (Appendix 1).

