7 PATIENTS AND SCREENING

In order to participate in this study the patients must meet all of the following inclusion criteria and must not meet any of the following exclusion criteria. Inclusion in the trial starts with the informed consent signature. Patients should only be permitted to screen for this study if they are free of any sub-clinical infection (indicated by the presence of an Eosinophil count below $0.3 \times 10^9/L$ within 1 month of screening). The inclusion and exclusion criteria are to be verified at the screening visit (Visit 1) and at the start of treatment/baseline visit (Visit 2).

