13. Patients with a history of clinically significant drug or alcohol abuse in the opinion of the investigator in the last year prior to Baseline (Day 0).
14. Patients who have participated in any other clinical study with an investigational drug within 3 months before the first day of administration of study treatment.
15. Patients who have had treatment with biologics as follows:
 - a. Any cell-depleting agents including but not limited to rituximab: within 6 months before the screening visit, or until lymphocyte count returns to normal, whichever is longer,

- b. Other biologics influencing cell proliferation: within 6 months before the screening visit.
16. Patients who are pregnant, planning pregnancy, breastfeeding and/or are unwilling to use adequate contraception (as specified in inclusion criterion 9) during the trial.
17. Patients, in the opinion of the investigator, not suitable to participate in the study.

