8 STUDY CONDUCT

8.1 Study Schedule

During the study, six visits to the clinic are scheduled at least one week after the screening visit: one at the start of the comparative treatment period/baseline (Day 0/Visit 2) and five in the comparative treatment period (Week 2/Visit 3, Week 4/Visit 4, Week 6/Visit 5 and Week 8/Visit 6). A final safety follow-up visit (Visit 7) will be conducted two weeks after Visit 6 or two weeks after the final visit attended if the patient does not complete the study. The baseline visit must be performed, at the latest 30 days after the screening visit.

Patients who discontinue the study early will be asked to attend the investigative site as soon as possible so that assessments scheduled for Visit 6 can be conducted at an Early Termination visit.

In the event that treatment is occurring, a wash out period of up to 4 weeks may be necessary. At the Screening visit, after giving informed consent to participate, patients will be assessed using the screening examinations. Eligible patients with confirmed AD using the Hanifin and Rajka criteria and who meet all the inclusion criteria and do not meet the exclusion criteria at the baseline visit will be enrolled.

During the treatment period and follow-up period patients will be restricted from using any other treatment for AD, with the exception of the same emollients they have been consistently using at the baseline visit. Any medication (prescription as well as OTC drugs) or therapeutic intervention deemed necessary for the patient, and which in the opinion of the Investigator do not interfere with the safety and efficacy evaluations, may be continued. A list of ‘medications and therapeutic regimens excluded from the study’ is defined below (Section 9.2.11.2).

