8.2.3 Baseline (Visit 2)

Note: it must be ensured that all inclusion regarding the severity of the disease remain unchanged since the screening in order to exclude patients reacting to the emollient use since screening visit. Patients will attend the investigational site at Visit 2 when the following procedures/assessments will occur.

- Verification of inclusion/exclusion criteria (Sections 7.2 & 7.3)
- Hanifin and Rajka criteria review (as detailed in Appendix 2 (15.2))
- Patient Randomisation (as detailed in Section 10.5)
- Samples for clinical laboratory safety tests (haematology, serum biochemistry, urinalysis as detailed in Section 9.2.4)
- Pharmacokinetic Sampling (as detailed in Section 9.2.7)
- Biomarker Sampling (as detailed in Section 9.2.8)
- Vital signs (blood pressures, heart rate and body temperature), as detailed in Section 9.2.3);
- Physical examination (as detailed in Section 9.2.2)
- Body Mass Index (as detailed in Section 9.2.6)
- Dispense Study Drug
- Dispense Patient Compliance Log
- Body Surface Area (as detailed in Section 9.1.4)
- Investigator's Global Assessment (as detailed in Section 9.1.1)
- Eczema Area and Severity Index (EASI) (as detailed in Section 9.1.2)
- NRS Pruritus assessment (as detailed in Section 9.1.3)
- Dermatology Life Quality Index (DLQI) Questionnaire (as detailed in Section 9.1.5)

- Patient Orientated Eczema Measure (as detailed in Section 9.1.6)
- Patient Global Impression of Severity Questionnaire as detailed in Section 9.1.7)
- Patient Global Impression of Change Questionnaire as detailed in Section 9.1.8)
- Concomitant medication assessment (as detailed in Section 9.2.11)

If all study entry criteria are satisfied the investigator will randomize the patient and provide the patient with the DS107 capsules or Placebo capsules from one of the patient treatment packs available at the site (allocated via the central randomization).

The first administration of DS107 or Placebo will be carried out after the Baseline visit. Following this DS107 capsules or Placebo medication will be administered once daily IMP will be administered approximately 2 hours after food consumption at the same time each day.

Patients will be given a compliance log to document administration of DS107 capsules or Placebo. Clinical staff will explain to the patient how to use the compliance log to document IMP administration compliance.

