8.2.7 Week 8 (Visit 6) / End of Treatment or Early Termination

Patients will return to the investigational site at Visit 6. **The last dose of DS107/Placebo should be taken the day before Visit 6.**

For accountability purposes, patients will be required to bring both the used DS107/Placebo patient packs and unused DS107/Placebo supplied at Visit 5. Patients will be required to provide the patient compliance log for confirmation of compliance.

The following procedures/assessments will occur:

- Samples for clinical laboratory safety tests (haematology, serum biochemistry, urinalysis as detailed in Section 9.2.4)
- Pharmacokinetic Sampling (as detailed in Section 9.2.7)
- Biomarker Sampling (as detailed in Section 9.2.8)
- Sample for pregnancy test (only female patients of child-bearing potential, as detailed in Section 9.2.5)
- Vital signs (blood pressures, heart rate and body temperature), as detailed in Section 9.2.3);
- Physical examination (as detailed in Section 9.2.2)
- Body Mass Index (as detailed in Section 9.2.6)
- Collect Study Drug
- Collect and Review Patient Compliance Log
- IMP Accountability (as detailed in Section 10.6)
- Body Surface Area (as detailed in Section 9.1.4)
- Investigator's Global Assessment (as detailed in Section 9.1.1)
- Eczema Area and Severity Index (EASI) (as detailed in Section 9.1.2)
- NRS Pruritus assessment (as detailed in Section 9.1.3)
- Dermatology Life Quality Index (DLQI) Questionnaire (as detailed in Section 9.1.5)
- Patient Orientated Eczema Measure (as detailed in Section 9.1.6)
- Patient Global Impression of Severity Questionnaire as detailed in Section 9.1.7)
- Patient Global Impression of Change Questionnaire as detailed in Section 9.1.8)
- Concomitant medication assessment (as detailed in Section 9.2.11)
- AE assessment (as detailed in Section 11)

The DS107or Placebo patient packs will be returned. No further DS107or Placebo patient packs or patient compliance logs will be issued. Following completion of the study assessments at this visit, there will be continued study restrictions in line with those described in sections 9.2.11 and 9.2.12.

An NRS for the assessment of pruritus will continue to be captured on a daily basis from baseline to the follow up visit. Emollient use will also continue to be captured on a daily basis for the same period.

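### Pregnancy must be ruled out again at Visit 2, but no test is scheduled there: the screening result can be 30 days old at randomisation, and the next test comes only after the last dose

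*Protocol*

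**What the plan says.** Exclusion 16 in Protocol section 7.3 rules out "Patients who are pregnant, planning pregnancy, breastfeeding and/or are unwilling to use adequate contraception". Section 7 sets when it is checked: "The inclusion and exclusion criteria are to be verified at the screening visit (Visit 1) and at the start of treatment/baseline visit". The Visit 2 procedure list in section 8.2.3 repeats the check and makes randomisation depend on it: "If all study entry criteria are satisfied the investigator will randomize the patient".

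The test schedule is narrower. Section 9.2.5 says that "a pregnancy test will be carried out at screening and Week 8 /Visit 6/ET visit". The procedure lists for Visit 1 (8.2.1) and Visit 6 (8.2.7) and the flow chart in Appendix 1 agree. The Visit 2 list has no pregnancy test, and the laboratory panel in Table 2 (section 9.2.4) contains no hCG. The SAP adds none.

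On timing, section 8.1 says "The baseline visit must be performed, at the latest 30 days after the screening visit". It also sets a minimum interval: "six visits to the clinic are scheduled at least one week after the screening visit". The flow chart, however, allows screening from Day -30 to Day -1. At the other end, section 8.2.7 says "The last dose of DS107/Placebo should be taken the day before Visit 6", and section 10.3 applies the same rule to the early termination (ET) visit.

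**The concern.** The decision to start dosing is taken at Visit 2. For pregnancy, the only objective evidence available then is the screening result. A site that follows the plan exactly can randomise and dose a woman who conceived after that test, or too shortly before it for the test to show.

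The long interval is part of the design. Section 8.1 foresees a wash-out of up to 4 weeks, and exclusion 2 requires 4 weeks off systemic treatment. Patients who need that wash-out are likely to have the oldest screening result.

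Once dosing starts, section 11.4 requires study drug to be stopped when a pregnancy is confirmed. That rule starts with the patient telling the site. No scheduled test supports it, so an unrecognised pregnancy could be exposed for the full 8 weeks.

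**Working it through.** The plan gives no figure to reproduce. The check is calendar arithmetic on the schedule.

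**Inputs from the protocol**
- Age of the screening test at Day 0: at most 30 days (8.1, flow chart); at least 7 days under 8.1, or 1 day if the flow chart's Day -1 is allowed.
- Next scheduled test: Day 56, window ±2 days (flow chart).
- Last dose: the day before that visit (8.2.7).

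**Assumption, not in the documents:** a test turns positive 10 to 14 days after conception.

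**Window of conceptions not detected at Day 0.** The window ends at Day 0, and its length is the age of the latest test plus the detection lag. With a test at Visit 2 the age is 0, so the window is 0 + 10 = 10 to 0 + 14 = 14 days in every case.

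| Age of screening test | Current plan | With Visit 2 test | Days removed | Share of window removed |
|---|---|---|---|---|
| 30 days | 30+10=40 to 30+14=44 | 10 to 14 | 30 | 30/44=68% to 30/40=75% |
| 7 days | 7+10=17 to 7+14=21 | 10 to 14 | 7 | 7/21=33% to 7/17=41% |
| 1 day | 1+10=11 to 1+14=15 | 10 to 14 | 1 | 1/15=7% to 1/11=9% |

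The number of days removed equals the age of the screening test and does not depend on the assumed lag; only the percentages do. They are shares of calendar days, not of pregnancies.

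**Longest gap between scheduled tests**
- Current plan: 30 + 56 = 86 days, or 88 with the +2-day window.
- With a Visit 2 test: 56 days, or 58 with the window.

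**Dosing period.** Eight weeks of once-daily dosing is 8 × 7 = 56 doses, with no scheduled pregnancy test between the first and the last.

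**The case against.** The strongest reply is that the protocol does not contradict itself. It nowhere says that exclusion 16 must be verified by a laboratory test. Parts of that criterion, such as planning a pregnancy or willingness to use contraception, can only be checked by history, and exclusion 6 is tied to a screening result. This stands: the point is a gap in the evidence for the re-check, not a conflict between sections.

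Second, inclusion 9 requires adequate contraception for the duration of the study, with hormonal methods stable for at least one month before baseline. This lowers the risk on every day counted above, and the documents do not allow the number of pregnancies to be estimated. That also stands. But the protocol does not rely on contraception alone at screening, and the same reasoning applies when dosing is decided.

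Third, 30 days is the worst case. Emollient run-in takes 7 days and topical wash-out 2 weeks, so many intervals may be shorter. The actual distribution is unknown, which is why the 7-day and 1-day cases are shown as well.

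Fourth, patients who leave early are tested sooner, at the ET visit. Their test still comes after dosing, because section 10.3 places the last dose the day before that visit too. A patient who stops drug but stays in follow-up (7.5.2) may be tested well after her last dose. Unscheduled visits allow medically necessary procedures, but nothing prompts one in a woman unaware that she is pregnant.

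Finally, the documents report no fetal-harm signal. Section 1.5 describes no embryo-fetal study either, so this argues neither for urgency nor for dismissal.

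**Conclusion.** The concern holds. The protocol lets a compliant site randomise on a pregnancy result up to 30 days old, and schedules no further test until after the last dose. At the maximum interval a Visit 2 test takes 30 days off the undetected-conception window; at the one-week minimum in section 8.1 it takes off 7. The remaining 10 to 14 days, under the assumed detection lag, cannot be removed by any test. The schedule facts and day counts come directly from the protocol; the window lengths and percentages rest on the lag. The expected number of pregnancies cannot be derived. The change is worth making because the gap is foreseeable and cheap to close, but it concerns participant safety only and leaves efficacy, power and error rates as they are.

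**What to change.** Add a rapid urine pregnancy test at Visit 2 for women of childbearing potential, with a negative result required before randomisation. It can use the urine already collected for urinalysis, but it must be read on site, because section 9.2.4 sends all samples to the central laboratory. Amend sections 8.2.3 and 9.2.5 and the Appendix 1 flow chart to match.

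The cost is wording in three places and one kit per woman of childbearing potential who reaches Visit 2: fewer than 300 at the planned size, plus those who fail at that visit. No extra visit or sample is needed. The downside is an occasional late screen failure.

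The Visit 2 test does not close the on-treatment gap. A separate, optional Week 4 test would cut the longest untested interval on drug from 56 to 28 days at nominal visit dates, for one more kit and urine sample at an existing visit.

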9.2.6 Body Mass Index (BMI)

Weight (kg) and Height (cm) will be collected to calculate the BMI (kg/m²), and will be recorded at Screening/Visit 1, Baseline/Visit 2 and Week 8/Visit 6/ET. The height will only be recorded once at the screening visit and the same value will be used for BMI calculation at Baseline/Visit 2 and Week 8/Visit 6 visits.

9.2.7 Pharmacokinetic Sampling

Blood samples for PK analysis will be collected via direct venepuncture as per the Study Flow Chart (Appendix 1) at Baseline/Visit 2, Week 4/Visit 4, Week 8/Visit 6/ET and Week 10/Visit 7/Follow up.

The detailed instruction for PK sample collection, processing, storage and shipment will be provided in a separate procedure.

9.2.8 Biomarker Sampling

Blood samples will be collected via direct venepuncture as per the Study Flow Chart (Appendix 1) at Baseline/Visit 2, and Week 8/Visit 6/ET and will be stored for the potential analysis of AD biomarkers at a later date.

The detailed instruction for biomarker sample collection, processing, storage and shipment will be provided in a separate procedure.

9.2.9 Sample Storage, Handling and Shipping

Sample storage, handling and shipping will be done as per standard operating procedures and as specified in the Laboratory Procedures Manual.

9.2.10 Adverse Event Assessment

See section 11.

9.2.11 Concomitant Medication

Any medication (prescription as well as over the counter (OTC) drugs, vitamins and antacids) or therapeutic intervention deemed necessary for the patient, and which, in the opinion of the Investigator, do not interfere with the safety and efficacy evaluations, may be continued unless they are included in the list of 'medications and therapeutic regimens excluded from the study' outlined below. However, the Investigator should be cautious in evaluating the need for change in dosage and should carefully assess if any concomitant medication is necessary.

Any medications, herbal medicines, natural health remedies and nutritional supplements used within 30 days prior to Screening (Visit 1) until completion (Visit 7) are to be recorded in the Concomitant medication module in the CRF system. The generic name of the medication (i.e., not local trade names), along with start date, stop date, dose, route, regimen and indication shall be recorded as applicable in the CRF system.

Any new medications or changes to the dose or regimen of pre-existing medications will be updated on a routine basis during the study.

Investigational new drugs (i.e. drugs that are not marketed in the local market) should not be co-administered with the IMPs during the entire period of the study.

9.2.11.1 Permitted Therapies

9.2.11.1.1 Emollients

All patients should be applying a bland emollient of their choice, **initiated at least 7 days prior to Baseline/Day 0**, twice a day on their skin including AD lesions. Emollient use must continue at the same frequency and on the same skin areas throughout the study. Patients will be requested to avoid using emollients containing any active ingredient which has or may have an effect on AD including the following ingredients:

- Urea
- Ceramide
- Hyaluronic acid

Every effort should be made to keep the same emollient throughout the study. The commercial name of the selected emollient(s) will be recorded in the source document and the eCRF, along with the frequency and quantity. Patients will also record on a daily basis their emollient use as instructed by the clinic staff. No other products may be applied to the lesions during the study.

9.2.11.1.2 Other Permitted Therapies

Non-sedative anti-histamines (e.g. loratadine, fexofenadine) are allowed during the study only if used to treat medical conditions other than AD. Such medications are allowed during the study only if the patient has been on a stable dose for at least 4 weeks prior to Baseline/Day 0 and continues to use the same agent everyday throughout the study

Inhaled and intranasal corticosteroids for stable medical conditions are allowed.

9.2.11.2 Medications and therapeutic regimens excluded from use in the study

The following topical therapies or procedures are prohibited during the study for all patients:

- Topical medicated treatments that could affect AD, including but not limited to:
 - topical corticosteroids
 - tars
 - bleach
- Any topical product containing urea, ceramides or hyaluronic acid
- Systemic therapy that could affect AD, e.g. retinoids, methotrexate, cyclosporine, hydroxycarbamide (hydroxyurea), azathioprine and oral/injectable corticosteroids
- Anti-histamines used for AD
- Any biological agent
- UV-A or UV-B phototherapy
- Psoralen + Ultraviolet A (PUVA) therapy
- Use of tanning booth
- Any other investigational medicinal product
- Traditional medicine, herbal extracts and supplements used to treat AD

9.2.12 Restrictions

Behavioural

Patients will be asked to refrain from any travel to sunny climates or use of tanning equipment, saunas and swimming throughout the duration of the study.

Extensive UV exposure or UV-B devices will be prohibited within 4 weeks of the start of the trial and during the trial.

Other

Patients will be instructed to abstain from using any drugs/treatments that may influence AD (refer to exclusion criteria and prohibited therapies or procedures section) throughout the study.

Patients will be required to administer the drug 2 hours after the consumption of food. Medication(s) for other conditions that are permitted in the study can be taken as usual.

